18.2 Report of Prior Investigations

Provided under separate cover.

18.3 Instructions for Use/Labeling

Provided under separate cover.

18.4 Sample Informed Consent Form

Provided under separate cover.

18.5 Training Plan

Provided under separate cover.

18.6 List of Monitors

Provided under separate cover.

18.7 List of Institutions

Provided under separate cover.

19. Version History

Version	Summary of changes	Author(s)/Title
1.0	Not Applicable, New Document	[REDACTED]
2.0	
Secondary Endpoints: Added to include 5-year follow-up for oncology subjectsUpdated stopping rules to ensure patient safety oversightUpdated exclusion criteria for oncology prostatectomy subjects 
Added roll-in phase to assess Hugo™ RAS System performance
	[REDACTED]
3.0	
Added primary effectiveness endpointUpdated Statistical Design and Methods section	[REDACTED]
4.0	
Updated definition of ConversionUpdated Clinical Study Design Justifications to include safety and effectiveness	[REDACTED]

Medtronic Expand URO Clinical Investigation Plan

MDT19051EINURO

Version 9.0

Page 110 of 111

Medtronic

Version	Summary of changes	Author(s)/Title
5.0	
During the review of the investigational plan, the FDA recommended to add performance goals for the secondary endpoints. As per the FDA, pre-specifications of performance goals for the secondary endpoints will help evaluate the benefit-risk profile for the investigational device to support the marketing approval. Following the recommendation, performance goals are specified for each of the secondary endpointsRemoved Steering Committee Member due to outside of the study conflict of interest not related to the trialChanged margin, tumor size, tumor stage and total lymph nodes retrieved to follow-up visit. Pathology takes 10-14 days to be returnedUpdated causality definitionsUpdated template versionSection 16.8.1: Updated requirements due to the combined guidelines	[REDACTED] [REDACTED] [REDACTED] [REDACTED]
6.0	
Updated template to Rev EUpdated to include a 6th site	[REDACTED] [REDACTED]
7.0	
Added an additional Steering Committee MemberUpdated definition of conversionUpdated Risk Section to match the new Risk Management Report.Added Anastomotic Leak Test (if applicable) to the schedule of eventsAdded Anastomotic Stricture (if applicable)	[REDACTED]

Medtronic Business Restricted

This document is electronically controlled

CONFIDENTIAL 056-F275 Rev E Clinical Investigation Plan Template

Medtronic Expand URO Clinical Investigation Plan

MDT19051EINURO

Version 9.0

Page 111 of 111

Medtronic

Version	Summary of changes	Author(s)/Title
8.0	
• Adverse Event reporting guidelines were updated• Administrative changes of commercial materials. We removed TUNVCA8STF and added ONB123TF and ONB5STF• Time to submit events to the CEC for adjudication has been removed to allow for more complete submissions.• Updated the definition of "complication rate" to align with that in published literature data that were used to determine performance goals• Updated sample sizes of the nephrectomy and prostatectomy cohorts• Updated the primary and secondary endpoint performance goals and clinical rationales for all three cohorts• Included the bibliography of publications utilized for the updated statistical design• Time to submit events to the CEC adjudication has been removed to allow for more complete submission	[REDACTED] [REDACTED] [REDACTED] [REDACTED]
9.0	
• Updated the publications supporting the statistical design for the performance goals for all three cohorts• Updated the Secondary performance goals for all three cohorts• Formatting edits• Text edits to provide clarification	[REDACTED]

Medtronic Business Restricted

This document is electronically controlled

CONFIDENTIAL 056-F275 Rev E Clinical Investigation Plan Template

2.0	
 Updates and clarifications were added throughout the document to be consistent with CIP 8.0 Moved extraneous details from section 4 to be included with the analysis descriptions in section 7.9 Added R version 4.0.0 as an allowable statistical software in section 7.2 Added sub-group analysis by surgery type to primary effectiveness analysis Added detail to section 7.9 to clarify the hypothesis, endpoint definition, performance requirements, performance requirements rationale, analysis methods, determination of subjects, and supporting analyses for all primary (Sections 7.9.1 and 7.9.2) and secondary objectives (Section 7.9.3). Analysis of ancillary objectives are also clarified in section 7.9.4 	[name], Senior Statistician [name], MS, Senior Principal Statistician
3.0	
 Made minor updates to be consistent with CIP V9.0: Added wording "up to" to attrition-adjusted sample sizes statements throughout the document to account for lower-than-expected attrition rates. Clarified the derivation of the time window for events in scope of the primary safety endpoint to be within 30 calendar-days post procedure (Section 7.9.2.2) Clarified the definition of the events in scope of the primary safety endpoint to be any CEC-adjudicated related (device, procedure, underlying condition/disease) adverse event (Section 7.9.2.2) Clarified secondary endpoint definitions involving the 30-day follow-up to refer to the 30 calendar-day post procedure to align with the primary safety endpoint (Section 7.9.3.1) Added an overview of the Holm-Bonferroni method (Section 7.5) Added confidence intervals as a general methodology (Section 7.2) 	[name], MS, Senior Principal Statistician

2. List of Abbreviations and Definitions of Terms

Abbreviation	Definition
AE	Adverse Event
ADE	Adverse Device Effect
CEC	Clinical Event Committee
CIP	Clinical Investigation Plan
CSR	Clinical Study Report
DD	Device Deficiency
eCRF	Electronic Case Report Form
FAS	Full Analysis Set
FDA	United States Food and Drug Administration
MedDRA	Medical Dictionary for Regulatory Activities
PG	Performance Goal
PPAS	Per Protocol Analysis Set
RAS	Robotic Assisted Surgery
SADE	Serious Adverse Device Effect
SAP	Statistical Analysis Plan
SAS	Statistical Analysis System
SOP	Standard Operating Procedure
UAE	Unavoidable Adverse Event
UADE	Unanticipated Adverse Device Effect

3. Introduction

Over the course of history, surgery has generally evolved towards less invasive methods for performing the same procedures. Presently, surgical technique is undergoing another revolution – the growth of robotic-assisted surgery (RAS). Much as the laparoscope changed how surgery was practiced in the 20th century, RAS will similarly propel forward surgical specialties in the 21st century. RAS is based on the accurate translation of user input to a robotically assisted output. Similar to laparoscopic surgery, RAS involves the use of endoscopic instrumentation for manipulation of tissues and vessels in the insufflated body cavity.

The Medtronic Hugo™ RAS System is a modular robotic platform for performing robotically assisted minimally invasive surgery. This clinical study will evaluate the safety and effectiveness of the Medtronic Hugo™ RAS System when used for urologic RAS.

The statistical analysis plan (SAP) specifies the statistical methods to be implemented for the analysis of data used in this clinical study. It elaborates on the statistical analyses specified in the Clinical Investigation Plan (CIP) version 8, Dated 15-NOV-2023 (the first 15-patient summary was based on CIP 4.0, dated 16-SEP-2021).

This document was created for internal use as a guideline for the study Biostatistician, Statistical Programmer(s), and other relevant stakeholders. Analysis results obtained from the statistical analyses outlined in this document will be the basis of the Clinical Study Report (CSR) for this study.

As with any statistical analysis plan, the proposed methods and approaches to the data analysis should be considered as flexible to accommodate necessary changes. Changes to the plan may arise if emerging data suggest that deviations from the original plan would provide a more reliable and valid analysis of the data. Sound statistical reasoning will substantiate any and all deviations from this plan. The purpose of this plan is to provide general, and in some instances, specific guidelines from which the analysis will proceed.

The planned analyses identified in this SAP may be included in regulatory submissions and/or future manuscripts. Additional exploratory analyses, not identified in this SAP, may be performed to support the clinical development program. Any post-hoc, or unplanned, analyses that are performed for the CSR, but not identified in this SAP, will be clearly delineated in the CSR.

4. Study Objectives

4.1 Primary Objective

The primary objective of this study is to confirm that the Medtronic Hugo™ RAS System is safe and effective when used for urologic robotic-assisted surgery.

4.1.1 Primary Effectiveness Objective

The primary efficacy objective of this study is to confirm that the Medtronic Hugo™ RAS System is effective when used for urologic robotic assisted surgery. The primary effectiveness endpoint is the surgical success rate, defined as the procedure not going into conversion. Conversion is defined as the switch from a robotic-assisted approach using the Hugo™ system to a robotic-assisted approach utilizing an FDA cleared robotic-assisted device, laparoscopic or open surgery.

4.1.2 Primary Safety Objective

The primary safety objective of this study is to confirm that the Medtronic Hugo™ RAS System is safe when used for urologic robotic assisted surgery. The primary safety endpoint is the rate of subjects with major complications from the first incision through 30 days post-procedure. A major complication is defined as Grade III or higher complication per the Clavien-Dindo Classification system.

4.2 Secondary Objective

The secondary objective is to demonstrate that the Medtronic Hugo™ RAS System performs as intended when used in urologic robotic assisted surgery. The secondary endpoints will assess the overall performance of the Medtronic Hugo™ RAS System when used for urologic robotic surgery.

The following short-term secondary endpoints to assess the overall safety and performance of the Medtronic Hugo™ RAS System when used for urologic robotic surgery will be assessed.

- Complication rate: Overall rate of subjects with one or more complications (Clavien-Dindo Grade I or higher), from the first incision through 30 days post-procedure
- Operative time
- Intraoperative estimated blood loss (mL)
- Transfusion rate
- Rate of device-related conversion
- Hospital length of stay
- Readmission rate (through 30 days)
- Reoperation rate (through 30 days)
- Mortality rate (through 30 days)
- Rate of device deficiencies

The following long-term secondary endpoints will be assessed through 5 years in oncologic subjects:

- Overall survival
- Progression-free survival
- Disease-free survival

4.3 Ancillary Objectives

Descriptive analyses of other pre-specified outcome measures beyond the primary and secondary objectives will be exploratory in nature and are not intended as a focus of the study for the evaluation of the study device.

The following data will be collected as applicable:

- Rate of negative surgical margins
- Lymph node yield
- Warm ischemia time
- Surgeon experience

5. Investigation Plan

This is a prospective, multicenter, single-arm pivotal study to be performed in up to 141 subjects undergoing a urologic RAS procedure using the Medtronic Hugo™ RAS System. Subjects without an oncologic indication will be followed for 30 days (+7 days) post procedure. Oncologic subjects will be followed through 5 years. This study will be conducted using up to six investigative sites in the United States of America (USA).

This study will have two phases, a roll-in phase and open enrollment phase. Two (2) sites will consecutively enroll a total of 15 subjects who will be treated with the Hugo™ RAS System as “roll-in cases”. These subjects will undergo the same preoperative and postoperative assessments (with the same schedule) as patients who are enrolled in the open enrollment phase. Outcomes through 30 days for the first 15 roll-

in cases will be provided in a summarizing fashion and provided to the FDA for initial review without statistical inferences. The roll-in subjects will be included in the primary analysis with the open enrollment subjects and for all required reports.

Following completion of the roll-in phase and sponsor approval, all sites will be allowed to enroll patients in the study. During the open enrollment phase, all patients enrolled will follow the Clinical Investigation Plan.

The expected study duration is approximately 5 years. The duration of individual subject participation will be approximately 67 days (-30 to 30+7) for non-oncologic subjects and 5 years for oncological subjects.

6. Determination of Sample Size

The sample size for the study was estimated based on the primary safety and effectiveness hypotheses.

Power calculations were performed using statistical software NCSS PASS 2023.

The effectiveness hypothesis is to test if the surgical success rate is above the performance goal. The surgical success rate is expected to be 90% or higher. The effectiveness performance goal is set to be 85%. A sample size of 126 subjects will provide more than 80% power at one-sided alpha of 0.025 (with an expected rate of 95.2% or higher in this study).

Safety was also considered for the sample size determination. The primary safety endpoint is major complication rate. A statistical hypothesis with a performance goal is specified for each of the three urologic procedures (nephrectomy, prostatectomy, cystectomy). The safety performance goals were determined based on analyses of published literature by taking into account clinically meaningful margins and statistical precisions. Each individual hypothesis was adequately powered with at least 80% power at an alpha level of 0.008 with multiplicity adjustment taken into consideration. The sample sizes for the three surgery types are up to: 55, 55, and 31 for nephrectomy, prostatectomy, and cystectomy, respectively. After taking 10% attrition into account the total number of subjects planned for this study based on the sample size calculations was up to 141 subjects. Full calculations for the safety sample sizes and the associated power for each urologic procedure are below.

Nephrectomy: The mean effect size is 0.029 with a 95% confidence interval of 0.022 to 0.038. The 95% prediction interval is 0.017 to 0.047. The 99% prediction interval is 0.014 to 0.058. A performance goal of 0.20, while greater than the predicted interval, broadly aligns with the upper limits for each nephrectomy study with a comparable study size (95% upper limits ranging from 0.100 to 0.539) and is clinically appropriate. A performance goal of 0.20, assuming a sample size of up to 55 (with 10% attrition n=49), one-sided alpha of 0.008 (Bonferroni Correction), and mean effect size of 0.029, results in a power of 95%.

Prostatectomy: The mean effect size is 0.029 with a 95% confidence interval of 0.016 to 0.051. The 95% prediction interval is 0.004 to 0.173. The 99% prediction interval is 0.002 to 0.316. A performance goal of 0.20 (20%), is clinically appropriate. A performance goal of 0.20, assuming a sample size of up to 55 (with 10% attrition n=49), one-sided alpha of 0.008 (Bonferroni Correction), and mean effect size of 0.029, results in a power of 95%.

Cystectomy: The mean effect size is 0.141 with a 95% confidence interval of 0.095 to 0.205. The 95% prediction interval is 0.047 to 0.354. The 99% prediction interval is 0.024 to 0.520. A performance goal of

0.45 (45%), is clinically appropriate. A performance goal of 0.45, assuming a sample size of up to 31 (with 10% attrition n=27), one-sided alpha of 0.008 (Bonferroni Correction), and mean effect size of 0.141, results in a power of 83%.

With the consideration of both effectiveness and safety, a total of up to 141 subjects are planned to be treated in this study. Up to six study sites will be used. To keep enrollment balanced, each study site will be allowed to enroll no more than 30% of the total population.

7. Statistical Methods

7.1 Study Subjects

7.1.1 Disposition of Subjects

Subject disposition will be illustrated in a CONSORT diagram. The number of subjects screened, treated, discontinued during the study, as well as the reasons for discontinuations will be summarized for all centers combined and each center separately. Disposition and reason for study discontinuation will also be provided as a by-subject listing. All demographics and baseline characteristics will be summarized using descriptive statistics.

7.1.2 Clinical Investigation Plan (CIP) Deviations

Protocol deviations will be summarized, listed and discussed in the study report.

7.1.3 Analysis Sets

The following populations will be considered for the analysis of data for this study:

Full Analysis Set

The full analysis set (FAS) is defined using the modified intent-to-treat (mITT) principle as all enrolled subjects for whom a Hugo™ RAS procedure was begun, with the beginning of a procedure defined as the first skin incision being made. In the event that a subject is consented, but the first incision does not occur (e.g., if the subject becomes ineligible during the timeframe between consent and the procedure day), that subject will not be considered part of the FAS. The FAS will be the primary analysis set for the evaluation of the primary and secondary endpoints.

Adverse Events (AEs) will be collected from the time of consent. AEs occurring in patients excluded from the FAS will be followed for 30 days post-consent through study exit and will be reported in a listing in the CSR. These AEs will not be included in the primary FAS analysis for either AE reporting or the analysis of the primary and secondary endpoints. The number and proportion of subjects experiencing each type of AE will be summarized by site, surgery type and overall for the FAS.

Per Protocol Analysis Set

The per protocol analysis set (PPAS) is a subset of the FAS including only those subjects without any major protocol deviations. Major deviation reasons are: "Enrolled subject did not meet enrollment criteria" and

“Unauthorized use of investigational device.” Reasons for exclusion of subjects from PPAS will be documented in tabular format and reported.

All enrolled subjects will be included in a subject disposition table indicating reasons for exclusion from the FAS and PPAS analysis sets.

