9.2 Subject Enrollment

A subject is considered enrolled in the study when the consent process is signed and dated. Screening data will not be collected for the study until the subject has been determined to be eligible for the study and signed consent (see **Section 10.2** for details). If the subject is consented prior to the day of surgery, a re-verification of eligibility will be signed off by the PI or Sub-I on the day of surgery. As soon as the surgical procedure has begun with the Medtronic Hugo™ RAS System, the subject must be followed

Medtronic Business Restricted

This document is electronically controlled

CONFIDENTIAL 056-F275 Rev E Clinical Investigation Plan Template

regardless of whether or not the subject completed the surgical procedure with the Medtronic Hugo™ RAS System. Subject enrollment will be consecutive at the institution according to required procedure types and eligibility criteria. See **Section 9.3** for additional details.

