14.9 Analysis Populations

The following populations will be considered for the analysis of data for this study:

Full Analysis Set

The full analysis set (FAS) is defined as all enrolled subjects in whom the Hugo™ RAS procedure is begun, defined as the first skin incision. This is also known as a modified intent-to-treat (mITT) population. In the event that a subject is consented, but the first incision does not occur (e.g., if the subject becomes ineligible during the timeframe between consent and the procedure day), that subject will not be considered part of the FAS. The FAS will be the primary analysis set for the evaluation of the primary and secondary endpoints.

AEs will be collected from the time of consent. AEs occurring in subjects excluded from the FAS will be followed for 30 days post-consent through study exit and will be reported in a listing in the clinical study report. These AEs will not be included in the primary FAS analysis for either AE reporting or the analysis of the primary and secondary endpoints. The number and proportion of subjects experiencing each type of adverse event will be summarized by site and overall for the FAS.

Per Protocol Analysis Set

The per protocol analysis set (PPAS) is a subset of the FAS including only those subjects without any major protocol deviations. Prior to data analysis, a protocol deviation listing will be produced and sent to the clinical manager/team for review in order to verify which subjects will be excluded from the PPAS. Reasons for exclusion of subjects from PPAS will be documented and reported.

All enrolled subjects will be included in a subject disposition table indicating reasons for exclusion from the FAS and PPAS analysis sets.

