7.9 Evaluation of Objectives

7.9.1 Primary Effectiveness Objective

The primary effectiveness endpoint is the surgical success rate, defined as the procedure not going into conversion. Conversion is defined as the switch from a robotic-assisted approach using the Hugo™ system to a robotic-assisted approach utilizing an FDA cleared robotic-assisted device, laparoscopic or open surgery.

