7.9.1.6 Determination of Subjects/Data for Analysis

The analysis of the primary effectiveness will be based on the FAS but following the mITT principle for the conversion endpoint by excluding any subject with that endpoint missing.

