8	Reoperation Rate	Reoperation through 30 days is identified in a subject if they experience a related (device, procedure, or underlying condition/disease) adverse event that resulted in treatment with a surgical procedure and the AE start date was prior to or during the 30-calendar days post-procedure.
9	Mortality Rate	Death through 30 days is identified as an AE that led to death which occurs during the procedure or up to the 30 calendar-days post-procedure.
10	Device Deficiencies	A subject is identified as experiencing a device deficiency if a device deficiency occurred before, during, or after the subject's procedure.
11	Overall Survival	Subject death will be identified as an adverse event that leads to death where the adverse event start date is on or after the procedure date or if the subject is noted by the site to have died during follow-up. Time to death will be calculated as the difference in days between death and the procedure date.
12	Progression-free Survival	Disease progression will be identified in a subject if their disease state is noted by the site, during follow-up, as "disease reoccurrence, disease progression", or if subject death had been noted. This is assessed as either at the time of the follow-up visit or at the time of last contact, whichever is earlier will be denoted as the time of disease

		progression. Time to disease progression is calculated as the difference in days between disease regression and the procedure date.
13	Disease-free Survival	Disease reoccurrence will be identified in a subject if the subject disease state is noted by the site, during follow-up, as “disease reoccurrence, disease progression”, “disease reoccurrence, disease stable”, or if subject death had been noted. This is assessed either at the time of a follow-up visit or at the time of last contact, whichever is earlier will be denoted as the time of disease reoccurrence. Time to disease reoccurrence will be calculated as the difference in days between disease reoccurrence date and the procedure date.

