7.9.3.6 Determination of Subjects/Data for Analysis

Subjects from the FAS with data available will be included for each secondary analysis. Secondary endpoint 2 will add the additional requirement that it will be for subjects who did not undergo conversion.

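### A subject switched away from Hugo before first incision because the system failed enters neither the surgical success rate nor the device-deficiency rate

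*SAP*

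**What the plan says.** Enrolment happens at consent. Protocol 9.2: "A subject is considered enrolled in the study when the consent process is signed and dated". The FAS starts later. Protocol 14.9 defines it as "all enrolled subjects in whom the Hugo™ RAS procedure is begun, defined as the first skin incision". SAP 7.1.3 has the same rule: "all enrolled subjects for whom a Hugo™ RAS procedure was begun, with the beginning of a procedure defined as the first skin incision being made". The SAP then deals with the subject described by "In the event that a subject is consented, but the first incision does not occur" and places that subject outside the FAS. The one example in both documents is a subject who becomes ineligible between consent and the day of surgery.

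The rates follow the FAS:

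- **Surgical success** (SAP 7.9.1.6): "The analysis of the primary effectiveness will be based on the FAS", less any subject whose conversion endpoint is missing.
- **Conversion** (SAP 7.9.1): "Conversion is defined as the switch from a robotic-assisted approach using the Hugo™ system to a robotic-assisted approach utilizing an FDA cleared robotic-assisted device", or to laparoscopic or open surgery. The definition does not say from what moment a switch counts.
- **Device deficiencies** (SAP 7.9.3.1, endpoint 10): a subject counts "if a device deficiency occurred before, during, or after the" procedure. SAP 7.9.3.6 sets the population: "Subjects from the FAS with data available will be included for each secondary analysis".
- **Additional AE and device-deficiency summaries** (SAP 7.10): also the FAS.

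For subjects outside the FAS, SAP 7.1.3 plans an AE listing and a disposition table giving the reason for exclusion. It plans no device-deficiency listing. Protocol 12.2 has deficiencies collected on an eCRF throughout the study.

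**The concern.** Leaving out a subject who became ineligible has nothing to do with the device. Leaving out a subject because the tower, console or an arm did not work at set-up depends on the performance under test. A switch at that point fits the words of the conversion definition; only the analysis set removes it.

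The deficiency rate then has an odd shape. A set-up fault that still allows a Hugo incision counts. A set-up fault that prevents one does not.

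At stake are the one formal effectiveness test (performance goal 85%) and, descriptively, the deficiency rate, which protocol 10.5 names among the measures of device performance. Neither document says how such a subject is classified, so the decision would be made after the event.

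**Working it through.** **Which sentence excludes the subject.** The sentence about no incision covers a subject who is not cut at all. The subject of interest is cut, but under another approach. Exclusion therefore rests on the preceding requirement that a Hugo procedure was begun. That is the natural reading, but the SAP should state it.

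**Path of the subject through the plan**

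| Place | Subject switched before incision for device failure |
|---|---|
| Enrolled (protocol 9.2) | Yes |
| FAS (protocol 14.9, SAP 7.1.3) | No |
| Surgical success rate (SAP 7.9.1.6) | No |
| Deficiency rate (SAP 7.9.3.6), deficiency summaries (SAP 7.10) | No |
| AE listing, disposition table (SAP 7.1.3) | Yes |
| Deficiency listing | None planned for non-FAS subjects |

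**Inputs.** Null success rate 0.85, exact test, one-sided alpha 0.025, expected success 0.952, evaluable n 126 out of up to 141, stated power 0.96 (protocol 14.4.1 and 14.7, SAP 6). The number of pre-incision failures, k, and their share of attempts, q, are assumptions; the documents give neither.

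**Rule.** With f failures in n subjects, p = P(Bin(n, 0.15) ≤ f). The test passes if p < 0.025.

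**The plan's own figure.** At n = 126 the largest passing f is 10 (116 successes, p = 0.0131). Power at 0.952 is P(Bin(126, 0.048) ≤ 10) = 0.9595, which reproduces the stated 0.96.

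**Near the boundary.** Add k omitted cases as failures, to numerator and denominator:

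| FAS result | k | Extended result | p | Passes |
|---|---|---|---|---|
| 10/126 | 0 | 10/126 | 0.0131 | Yes |
| 10/126 | 1 | 11/127 | 0.0245 | Yes |
| 10/126 | 2 | 12/128 | 0.043 | No |
| 12/138 | 0 | 12/138 | 0.020 | Yes |
| 12/138 | 1 | 13/139 | 0.035 | No |
| 12/138 | 3 | 15/141 | 0.087 | No |
| 12/141 | 0 | 12/141 | 0.0157 | Yes |
| 12/141 | 1 | 13/142 | 0.0278 | No |

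**At the expected rate.** 126 × 0.048 ≈ 6 failures. With k = 5 the result is 11/131, p = 0.018, which passes. With k = 6 it is 12/132, p = 0.032, which does not.

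**Error rate across all attempts.** Suppose success over all attempts is exactly 85% and a share q fails before incision. Success within the FAS is then 0.85/(1 − q), and the FAS test at n = 126 rejects with probability 0.0245 (q = 1%), 0.045 (q = 2%), 0.079 (q = 3%) or 0.215 (q = 5%). The test at n = 126 has an actual size of 0.0131, so in this illustration the nominal 0.025 is exceeded at 2% and above but not at 1%.

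**Deficiency rate.** SAP 7.9.3.5 summarises endpoint 10 by surgery. One added case is worth about 1/55 = 1.8 points for nephrectomy or prostatectomy and 1/31 = 3.2 points for cystectomy, against a descriptive benchmark of 20%.

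**The case against.** An incision-based modified intention-to-treat set is stated consistently in both documents and is a legitimate choice. A failure that forces a switch after incision is counted as a conversion, and device-related conversion is a separate endpoint (SAP 7.9.3.1, endpoint 5). Only failure between consent and incision is left out, and such a case would be visible in the disposition table and could be recorded on the deficiency form. All of this stands, and it limits the point to a gap in the rates; the failure itself would not go unrecorded.

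Three stronger readings are tempting, and the documents do not support them:

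- **That the success rate is overstated.** This is true only if such cases occur. With none, nothing changes. The boundary examples are also unlikely results at the planned 95.2%.
- **That the word before in endpoint 10 contradicts the FAS restriction.** It has a use within the FAS: a set-up fault in a subject who then proceeds on Hugo. The text is incomplete for the switched subject, but not contradictory.
- **That the plan misses the clearest device failures, so the secondary objective cannot be judged.** Failures after incision are counted, and the documents do not show that failures before incision are the more important group.

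A further fair objection concerns comparability. The 85% goal comes from published conversion rates, and nothing shows that those include switches before the start. That is a good reason to leave the primary test alone. It does not prevent a supportive figure from being reported with that caveat.

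**Conclusion.** The point holds in conditional form. As written, an eligible subject switched from Hugo before incision because of a device failure enters neither the success rate nor the deficiency rate, and that exclusion depends on the device. Any such cases would push success up and the deficiency rate down.

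The effect on the formal test is material only close to the boundary: two omitted cases reverse a just-passing result on a FAS of 126, and one does so on a FAS of 138 or 141. At the expected 95.2% it takes six on a FAS of 126. The deficiency rate is not tested, so the effect there is descriptive. These sizes assume that each omitted case is scored as a failure and added to the denominator; how many cases to expect cannot be derived from the documents. This is a worthwhile, inexpensive improvement to a design choice. The primary analysis is not in error.

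**What to change.** Keep the FAS and the primary test unchanged. In the SAP, before database lock:

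1. **7.1.3:** state that a subject switched from Hugo before first incision is outside the FAS because no Hugo procedure was begun.
2. **7.9.1.7:** add one supportive analysis of the FAS plus every consented, eligible subject switched from Hugo to another approach before incision because of a device deficiency, with those added subjects scored as not successful.
3. **7.9.3.6:** report endpoint 10 on this extended set as well as on the FAS.
4. **7.10:** list device deficiencies for non-FAS subjects alongside the AE listing already planned.

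The cost is SAP wording, one flag, one table and one listing. The flag (Hugo set-up begun, and approach then used) may have to be confirmed from the deficiency form and the disposition reason, because neither document shows a dedicated field for it. The supportive success rate may be slightly lower than the primary one, and it may not be strictly comparable with the literature-based 85% goal; the report should say so. If no such case occurs, the table records that.
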